- Whether the event required treatment
- Outcome of the event
- 1259

1260 10.13 Planned Interim Analyses

Formal interim efficacy analyses are not planned as it is anticipated that recruitment will be completed prior to having sufficient outcome data for a meaningful analysis. Safety analyses will be performed at least every 6 months for review by the DSMB.

12641265 10.14 Pre-planned Sub-Group Analyses

Subgroup analyses/assessments of effect modification (interaction) will be conducted for the primary outcome. These analyses will be considered exploratory. Additionally, interpretation of the analyses will depend on whether the overall analysis demonstrates a significant treatment group difference; in the absence of such an overall difference, subgroup analyses will be interpreted with additional caution. The general approach for these exploratory analyses will be to add an interaction term for the subgroup factor by treatment into the models used for the primary analyses. The baseline factors listed below will be assessed.

- 1273 Age
- Age at T1D diagnosis
- Baseline time spent < 70 mg/dL
- Baseline glycemic variability (coefficient of variation)
- Baseline HbA1c
- 1278 T1D duration
- 1279 Gender
- 1280 Race-ethnicity
- Baseline scores on cognitive measures
 - Baseline assessment of hypoglycemic unawareness
 - Preserved C-peptide at baseline

1285 10.15 Multiple Comparison/Multiplicity

- 1286 The primary analysis involves a single treatment arm comparison for just one primary efficacy endpoint, 1287 so no correction for multiple comparisons will be performed.
- 1288

1282

1283

1284

- 1289 For the secondary analyses, the false discovery rate will be controlled using the adaptive Benjamini-
- 1290 Hochberg procedure.
- 1291

1292 **10.16 Exploratory Analyses**

1293 An outcome combining hypoglycemia and hyperglycemia measures will be assessed and defined further in 1294 the SAP.

1295 10.17 Additional Tabulations and Analyses

1296 Analysis on 16-week data will parallel the 26-week analyses with regard to CGM metrics and HbA1c. 1297

Analysis of all primary and secondary outcomes and the number of severe hypoglycemic adverse events will be replicated separately for pump users and MDI users. The interpretation of the analyses will depend on whether the overall analysis demonstrates a significant treatment group difference; in the absence of such an overall difference, this analyses will be interpreted with caution.

1302

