- Tabulation of visit and phone contact completion rates for each follow-up visit
- Tabulation of protocol deviations
- Tabulation of modifications in diabetes management during the study insulin regimen
 change or change in use of non-insulin medications for blood glucose control
- Tabulation of number and reasons for unscheduled visits and phone calls
- Tabulation of device issues

377 11. Baseline Descriptive Statistics

Appropriate summary statistics will be tabulated by treatment group for the following baselinedemographic and clinical characteristics.

- 380 Age381 Baseline time spent < 70 mg/dL
- Baseline glycemic variability
- Baseline HbA1c
- T1D duration
- Age at diagnosis
- Gender
- **387** Race-ethnicity
- Highest level of education
- Annual household income
- 390• Insurance status
- 391• Insulin delivery method
- Total daily dose of insulin/kg
- **393** Previous CGM use
- History of severe hypoglycemic event in past 12 months
- Preserved C-peptide at baseline
- 396 **12. Device Issues**
- 397 For each reportable device issue, the following will be tabulated:
- **398** Type of device
- **399** Type of device issue
- Onset date of the event
- If the issue was related to an AE
- If it was not related, the likelihood an AE could have occurred

 $F:\label{eq:studies} \label{eq:studies} F:\label{eq:studies} F:\label{eq:studies} F:\label{eq:studies} F:\label{eq:studies} F:\label{eq:studies} \label{eq:studies} F:\label{eq:studies} F:\label{eq:studies} F:\label{eq:studies} F:\label{eq:studies} F:\label{eq:studies} \label{eq:studies} F:\label{eq:studies} \label{eq:studies} F:\label{eq:studies} \label{eq:studies} F:\label{eq:studies} F:\label{eq:studies} \label{eq:studies} F:\label{eq:studies} \label{eq:studies} F:\label{eq:studies} \label{eq:studies} \label{eq:studies} F:\label{eq:studies} \label{eq:studies} F:\label{eq:studies} \label{eq:studies} \label{eq:studies} F:\label{eq:studies} \label{eq:studies} \label{eq:studies} \label{eq:studies} F:\label{eq:studies} \label{eq:studies} \label{eq:studies} \label{eq:studies} \label{eq:studies} F:\label{eq:studies} \label{eq:studies} \labe$

Whether the event met the definition for an Unanticipated Adverse Device Effect (UADE)

405 13. Planned Interim Analyses

Formal interim efficacy analyses are not planned as it is anticipated that recruitment will be
completed prior to having sufficient outcome data for a meaningful analysis. Safety analyses

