will be performed at least every 6 months for review by the DSMB.

409 **14. Pre-planned Sub-Group Analyses**

- 410 Subgroup analyses/assessments of effect modification (interaction) will be conducted for the
- 411 primary outcome. These analyses will be considered exploratory. Additionally, interpretation of
- the analyses will depend on whether the overall analysis demonstrates a significant treatment
- 413 group difference; in the absence of such an overall difference, subgroup analyses will be
- 414 interpreted with additional caution. The general approach for these exploratory analyses will be
- to add an interaction term for the subgroup factor by treatment into the models used for the
- 416 primary analyses.
- 417 The baseline factors listed below will be assessed. The p-value for any categorical variable will
- 418 only be calculated if there are a minimum of 10 subjects per treatment.
- 419 Age
- Baseline time spent < 70 mg/dL
- Baseline glycemic variability (coefficient of variation)
- Baseline HbA1c
- T1D duration
- Age of Diagnosis
- Gender
- Race-ethnicity (White non-Hispanic vs. non-White)
- Education (Some college or less vs, college graduate or more)
- Baseline scores on cognitive measures
- Baseline assessment of hypoglycemic unawareness (Aware/Uncertain vs. Reduced
 Awareness)
- Detectable C-peptide at baseline
- Number of SH events in the previous 12 months (0 vs. \geq 1)

433 15. Multiple Comparison/Multiplicity

- The primary analysis involves a single treatment arm comparison for just one primary outcomemeasure, so no correction for multiple comparisons will be performed.
- 436 For the secondary analyses, the false discovery rate will be controlled using the adaptive
- 437 Benjamini-Hochberg procedure. For these analyses, the adjusted p-value and 95% confidence
- 438 interval will be reported. The categories for FDR correction will be:

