- 470 (not separated for day and night) and total scores for questionnaires (not subscales) will be
- 471 included. The interpretation of the analyses will depend on whether the overall analysis
- 472 demonstrates a significant treatment group difference; in the absence of such an overall
- 473 difference, this analyses will be interpreted with caution. Only those who did not switch insulin

 $F:\label{eq:studies} \label{eq:studies} F:\label{eq:studies} F:\label{eq:studies} F:\label{eq:studies} F:\label{eq:studies} F:\label{eq:studies} \label{eq:studies} F:\label{eq:studies} F:\label{eq:studies} \label{eq:studies} F:\label{eq:studies} \label{eq:studies} F:\label{eq:studies} F:\label{eq:studies} \label{eq:studies} F:\label{eq:studies} \label{eq:studies} F:\label{eq:studies} \label{eq:studies} F:\label{eq:studies} \label{eq:studies} F:\label{eq:studies} \label{eq:studies} \label{eq:studies} F:\label{eq:studies} \label{eq:studies} \label{eq:studies} F:\label{eq:studies} \label{eq:studies} \label{eq:studies} \label{eq:studies} F:\label{eq:studies} \label{eq:studies} \label{eq:stu$

- delivery method during the RCT phase will be included and where a participant is using both
- 475 pump and injections, they will be considered a pump user.

476 17.3. BGM Checks

477 At each visit the average number of BGM measurements over the previous 7 days is recorded in

- the case report form. The average number of BGM checks per day will be calculated as follows
- 479 for baseline and follow-up:
- Baseline: We will prioritize the download value at the randomization visit, but if that is not available we will use the download at screening visit, and then if that is not available, the self-report at the screening visit.
- Follow-up: The data from each visit will be averaged to give an overall average number
 of BGM measurements per day. Priority will be given to downloaded data but self reported data will be used if downloaded data are missing.

486 The median and IQR of average number of BGM checks/day will be tabulated by treatment

487 group at baseline and follow-up. Treatment group comparison will be done using a longitudinal

linear regression model with the BGM checks at baseline and follow-up as the dependent
variable. This model will adjust for site as a random effect. If values are highly skewed then a

490 transformation or a non-parametric method based on ranks will be used instead.

491 17.4. CGM Group

492 Frequency of CGM Use

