550 Insulin dose, number of short-acting injections for injection users, and number of bolus doses for

pump users will be compared between treatment groups using a direct likelihood model similar

to the primary outcome. A longitudinal linear regression model will be fit with the summary

score at baseline and 26 weeks as the dependent variable. All models will adjust for site as a

- random effect and the insulin dose model will also adjust for insulin delivery method. Only
- subjects who do not switch insulin method during phase the RCT phase will be included. The
- analysis will report the p-value for the pairwise treatment group differences at 26 weeks.
- Residual values will be examined for an approximate normal distribution. If values are highlyskewed then a transformation or a non-parametric method based on ranks will be used instead.
- The false discovery rate will be controlled using the adaptive Benjamini-Hochberg procedure. Acorrection category will be added for these insulin comparisons.

561 20. References

- Beyond A1C Writing Group. Need for regulatory change to incorporate beyond A1C
 glycemic metrics. Diabetes Care. 2018;41:e92-e94.
- Danne T, Nimri R, Battelino T, et al. International consensus on use of continuous
 glucose monitoring. Diabetes Care. 2017;40:1631-1640.
- 566 3. The Juvenile Diabetes Research Foundation Continuous Glucose Monitoring Study
 567 Group. Continuous glucose monitoring and intensive treatment of type 1 diabetes. N Engl
 568 J Med. 2008;359(14):1464-76.

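### The pump-only and MDI-only analyses drop participants who switch insulin delivery after randomisation, and no planned analysis tests whether the CGM effect differs by delivery method

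*Protocol*

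**What the plan says.** Protocol 10.17 states that all primary and secondary outcomes, and the count of severe hypoglycaemic events, "will be replicated separately for pump users and MDI users". It excludes nobody on the ground of a change in delivery method.

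SAP 17.2 repeats that plan and adds a restriction: "Only those who did not switch insulin" "delivery method during the RCT phase will be included and where a participant is using both" pump and injections, that person counts as a pump user. The table of changes from the protocol in SAP 2 has one entry, the definition of nighttime. SAP 19 applies a similar rule to its post hoc insulin comparisons: only "subjects who do not switch insulin method during phase the RCT phase will be included".

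For effect modification, Protocol 10.14 and SAP 14 plan "to add an interaction term for the subgroup factor by treatment into the models used for the" primary analyses, and then: "The baseline factors listed below will be assessed". Neither list contains insulin delivery method, although SAP 11 tabulates "Insulin delivery method" as a baseline characteristic.

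The caution clause in Protocol 10.17 and SAP 17.2 applies only when the overall analysis shows no significant difference. In that case, in the absence of such a "difference, this analyses will be interpreted with caution".

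Protocol 10.3 and SAP 4 describe the separate pump and injection analyses as important and give them as one of two reasons for choosing 200 participants. The other is incomplete follow-up.

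**The concern.** There are two related weaknesses.

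**Who is in the analysis set.** Whether a participant switches is known only after randomisation, and it could depend on the arm. The trial is open-label. Staff review glucose data and recommend management changes at visits (Protocol 5.2.1). In the CGM arm those data include real-time CGM, whereas blinded sensor data from the BGM arm are withheld (Protocol 4.6 and 5.3). If switching depends on both arm and outcome, the retained participants are no longer comparable as randomised.

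**How the two strata are compared.** Two separate tests do not test a difference between strata. If the trial is positive overall, one stratum reaches significance and the other does not, the plan has no estimate of the difference with which to answer a claim that CGM works in only one group. The caution clause is not triggered in that case.

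At stake is the reading of analyses that helped to set the sample size. The primary result is not at stake.

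**Working it through.** **Inputs from Protocol 10.3 and SAP 4:** control mean 6%, 50% reduction (3 points), SD 5 points, two-sided 5%, 1:1 allocation, 180 completers. Protocol 1.5.4 sets a floor of 40% for each delivery method, so the completers could split 90/90 or, at the floor, 108/72 (0.40 × 180 = 72).

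**1. The plan's own figure.** Normal approximation per arm: 2 × (1.960 + 0.842)² × 5² / 3² ≈ 43.6, so 44 per arm and 88 in total. The noncentral t calculation gives 90 in total, with power 80.4%. The stated figure of 90 for 80% power is reproduced.

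**2. Discordant significance with the same true effect.** Power for a 3-point effect is 0.804 with 90 participants, 0.871 with 108 and 0.709 with 72. The chance that exactly one of two independent tests is significant is p(1 − q) + q(1 − p):
- 90/90: 2 × 0.804 × 0.196 = 0.315, about 32%.
- 108/72: 0.871 × 0.291 + 0.709 × 0.129 = 0.345, about 35%.

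These use unadjusted 5% tests.

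**3. Direction and size of selection bias (illustrative).** The documents give neither switch rates nor outcomes of switchers. Assume arm means of 3 (CGM) and 6 (BGM), with switchers averaging 8 and 10. The retained mean is (arm mean − rate × switcher mean) / (1 − rate).

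| Switch rate CGM / BGM | Retained CGM | Retained BGM | Effect | Bias |
|---|---|---|---|---|
| 10% / 3% | (3 − 0.8)/0.90 = 2.44 | (6 − 0.3)/0.97 = 5.88 | 3.43 | +0.43 |
| 3% / 10% | (3 − 0.24)/0.97 = 2.85 | (6 − 1.0)/0.90 = 5.56 | 2.71 | −0.29 |
| 2% / 2% | (3 − 0.16)/0.98 = 2.90 | (6 − 0.2)/0.98 = 5.92 | 3.02 | +0.02 |

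(Effects are computed from unrounded means.)

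A second model assumes no true effect, SD 5, and switching driven by a latent variable correlated 0.3 to 0.5 with the outcome. Equal 5% switching gives a false difference of 0. Rates of 2% (CGM) and 10% (BGM) give 0.2 to 0.4 points against CGM. The more extreme 2% and 20% give about 0.5 to 0.75 points against CGM.

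**4. Power lost to the exclusion.** If 5%, 10% or 15% switch, power in a stratum of 90 falls from 80% to 78%, 76% or 74%. In a stratum of 72 it falls from 71% to 69%, 66% or 64%.

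**5. What an interaction term would deliver.** SE = 5 × √(4/n₁ + 4/n₂).
- 90/90: 5 × √(8/90) = 1.49. The 95% CI half-width is 1.96 × 1.49 ≈ 2.9 points, and the smallest interaction detectable with 80% power is 2.80 × 1.49 ≈ 4.2 points. Power is 52% for a 3-point interaction and 17% for 1.5 points.
- 108/72: SE 1.52, detectable interaction 4.3 points, power 51% and 17%.

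**The case against.** Several points on the other side have force.

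- **The bias is not established.** A reader might infer that the rule inflates the CGM effect. The documents do not support that: they give no switch rate, and exchanging the two assumed rates turns an increase into a decrease. Only openness to bias can be claimed.
- **Switching will be partly visible.** SAP 10 tabulates insulin regimen change by treatment group, so a reader may see whether switching was common or unequal. That helps to diagnose the problem but does not restore the excluded participants.
- **The discordance figure is not the rate under the planned procedure.** A reader might take 32% to 35% that way. SAP 15 applies adaptive Benjamini-Hochberg within separate pump and MDI categories, so the planned rate will differ. The figure shows only how readily separate tests disagree by chance.
- **The plan does not claim that the effects differ.** It asks for an estimate in each population. But the two sets of significance results will stand side by side without an estimate of their difference.
- **Chapter 10 of the protocol is a framework.** Protocol 10.1 leaves detail to the later plan, so SAP 17.2 need not be read as contradicting 10.17. Even so, the restriction changes who is analysed, and SAP 2 is where such a change would be declared.
- **SAP 19 is different.** Injection counts and bolus counts are not comparable once a person has changed method, so excluding switchers from those comparisons is sensible. That section is also labelled post hoc.

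**Conclusion.** The point holds for the pump and MDI analyses in SAP 17.2. The no-switch restriction is an undeclared post-randomisation exclusion that leaves them open to bias of unknown sign and size: near zero if switching is rare or balanced, and roughly −0.3 to +0.4 points on a 3-point effect under assumed rates of 3% and 10%. All switch rates and switcher outcomes used here are assumptions.

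Separately, no planned analysis estimates the difference between the pump and MDI effects. With equal true effects under the plan's own inputs, the two tests would disagree in about 32% (90/90) to 35% (108/72) of trials before false discovery rate adjustment.

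A reader might go further and doubt the trial's main conclusion. The documents do not support that, because Protocol 10.5 and SAP 7.1 include all randomised participants in the primary analysis. Since these are secondary analyses, this is a point that should be fixed and not a fatal one.

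**What to change.** - **SAP 17.2:** classify every randomised participant as pump or MDI by delivery method at randomisation and keep all of them. Use the non-switcher set only as a sensitivity analysis.
- **Protocol 10.14 and SAP 14:** add insulin delivery method at randomisation to the list of baseline factors. Report the treatment-by-delivery interaction with its 95% CI as the comparison of the two strata, and state its low power (about 52% for a 3-point interaction), so that a non-significant result is not read as evidence of equal effects.
- **SAP 2:** list any no-switch rule that remains.
- **SAP 19:** leave the injection-count and bolus-count comparisons as they are.

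The cost is revised wording and one more model term on data already collected. The drawback is slight dilution of the stratum estimates by participants who change method; the sensitivity analysis would show how much that matters.
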